8.2 STATISTICAL ANALYSES

Definitions will be implemented as in section 8.1.3. Patients who are known to be alive at the date of data collection (1-year for interim report and 3-year for full study report) will be censored at the date of data collection, and patients who are lost to follow-up will be censored on the date they were last known to be alive (e.g., date of last recorded hospital visit). Patients who are alive and free from disease progression at the date of data collection and those lost to follow-up will be censored on the date they were last known not to have disease progression (i.e., the date of last documented response assessment). Patients remaining in CR or PR at the end of the post-initiation observation period or lost to follow-up will be censored on the date CR or PR was last documented.

[figure not shown]
[figure not shown]
Note: Some analyses that were originally proposed were not conducted as per the decisions of the CI and Pfizer team, these have been kept in this section as a record.

8.2.1 Primary Objective: To describe patient demographic and clinical characteristics at initiation of palbociclib.

Proposed: Age, duration of MBC prior to palbociclib (calculated by subtracting the date of initial BC diagnosis from the date of palbociclib initiation), number of lymph nodes involved, tumour size at initial disease diagnosis and Ki67 values will be summarised as quantitative variables (see section 8.1.1) using measures of central tendency (mean and median) and dispersion (standard deviation, interquartile range [IQR] and range) will be calculated. All other variables analysed as part of the primary endpoint, whether categorical or binary, will be presented as frequencies and percentages.

Actual: Age was presented as both a quantitative variable as per section 8.1.1 and as a categorical variable (Categories: Less than 40 years old, between 40 and 50 years old,

PFIZER CONFIDENTIAL

[figure not shown]
between 50 and 65 years old and aged 65 and over). Disease free interval was defined as the time from last known date the patient was on (neo)adjuvant hormone therapy to the date of metastatic breast cancer diagnosis (non de novo patients only). Disease free interval was presented as a categorical variable as per section 8.1.2 (Groups: less than or equal to 12 months and greater than 12 months). Time from letrozole to palbociclib initiation was presented as a quantitative variable as per section 8.1.1 for the first line palbociclib added group only. Time from letrozole was calculated by subtracting the start date of letrozole (ongoing at palbociclib initiation) from the date of palbociclib initiation. Number of metastatic sites was presented as a categoric variable as per section 8.1.2 (Groups: 1,2,3, 4 or more). Number of lines of prior endocrine therapy and chemotherapy prescribed for metastatic disease were presented as quantitative variables as per section 8.1.1. All other variables, aside from those named in this paragraph or the paragraph directly above were analysed as categoric variables as per section 8.1.2.

8.2.2 Secondary Objective 1: To describe treatment pattern (as per licence/IPP requirement); including the proportion of patients with dose modification and who switch treatment at 1 and 2 years after palbociclib initiation, and median time to dose modification and treatment discontinuation ('drug survival'). For patients who progress, to describe the 1st /2nd /3rd line of treatment after progression.

Proposed: Starting and mean dose of palbociclib and subsequent treatments after progression, length of treatments and time to dose reduction and discontinuation of palbociclib in days will be summarised as quantitative variables (see section 8.1.1). Times will be calculated in days through subtracting the time of first dose reduction/discontinuation from the date of palbociclib initiation. Treatment after progression and reasons for discontinuation, the proportion of patients completing a daily cycle, having dose reductions, treatment discontinuation and being co-administered letrozole and fulvestrant at palbociclib initiation will be summarised as categorical variables using frequencies and percentages (see section 8.1.2). Reasons for discontinuation of palbociclib will be presented as categorical data (see section 8.1.2) The proportions of patients with dose reductions and discontinuation will be calculated separately at 1 and 2 years after palbociclib initiation. Quantitative discrete variables (such as the number of completed cycles per patient) will be summarised using a combination of the approaches described in sections 8.1.1 and 8.1.2, if appropriate.

Actual: Starting dose of palbociclib was presented as a categoric variable as per section 8.1.2. Endocrine partner prescribed alongside palbociclib, proportion of patients with recorded dose reductions, proportion of patients who discontinued palbociclib and the associate reasons, proportion of patients with temporary interruptions to palbociclib treatment were presented as categoric variables as per section 8.1.2. Time to dose reduction was presented as a categoric variable as per section 8.1.2 (Categories: Patient did not have a dose reduction, dose reduction occurred within 3 months of palbociclib initiation, dose reduction occurred between 3 and 6 months after palbociclib initiation and dose reduction occurred over 6 months after palbociclib initiation). Number of patients

PFIZER CONFIDENTIAL

prescribed treatment in the 1st, 2nd, and 3rd line after palbociclib discontinuation was presented as a categoric variable as per section 8.1.2. Dose, duration of subsequent treatments and number of completed 28-day cycles per patient were presented as quantitative variables as per section 8.1.1. Number of completed 28-day cycles (categories: 1-6 cycles, 7-12 cycles, 13-18 cycles, 19-24 cycles, 25-27 cycles and No completed cycles) and the proportion of patients co-administered letrozole or fulvestrant were presented as categoric variables as per section 8.1.2. All other endpoints were evaluated as proposed.

8.2.3 Secondary Objective 2: To describe overall survival and progression-free survival, response (CR, PR), stable disease. This includes estimating the proportion of patients achieving those endpoints at 1 and 2 following palbociclib initiation: median survival, time to response and duration of response. In patients who respond to treatment, to describe PR and CR using “swimmer plots”.

Proposed: For the estimation of the proportion of patients alive, and free from disease progression, the denominator will be all patients known to be alive at the selected time-points (e.g., 1 years, 2 years, and 3 years). For the estimation of the proportion of patients achieving PR, CR and with stable disease at the selected time-points (1 years and 2 years), the denominator will be all patients with at least one assessment of response (CR / PR / no response or stable disease / progressive disease) in the past year.

[figure not shown]
Actual: Proportion of patients free from disease progression, are alive, achieved PR, CR or stable disease were analysed separately at the 2-year timepoint only. Length of follow-up, and time to best response and first response were presented as quantitative variables as per section 8.1.1. Best response to palbociclib, overall and by de novo and relapse status was treated as a categoric variable and analysed according to section 8.1.2.

8.2.4 Secondary Objective 3: To describe the occurrence of neutropenia during the first-year post-initiation observation period.

Proposed: The proportion of patients developing neutropenia and febrile neutropenia in the first 6 months post-palbociclib initiation will be summarised as a binary variable (see section 8.1.3), while occurrences per patient will be summarised as a quantitative variable (see section 8.1.1). Analyses for occurrences of neutropenia will be analysed overall and sub-divided by grade. Incidences of neutropenia will be presented in two ways. Firstly, neutropenia in the 6 months post-palbociclib initiation will be presented. Absolute neutrophil count, recorded as part of full blood counts or as part of the neutropenia dataset collected, will be used to determine incidences of neutropenia according to the CTC version 2.0 criteria (http://www.eortc.be/services/doc/ctc/ctcv20_4-30-992.pdf]).

Only absolute neutrophil counts from the neutropenia dataset that are within 6 months of palbociclib initiation will be included. Secondly, incidences of neutropenia as recorded in the notes will be presented as a quantitative variable (see section 8.1.1). The time from palbociclib initiation to first incidence of neutropenia will be presented as a quantitative variable (see section 8.1.1) with the categories to be determined after visualisation of the data.

PFIZER CONFIDENTIAL

Actual: Neutropenia, overall and by grade, was presented from two different sources on the eCRF (as recorded in the notes and inferred from the ANC measurements recorded in the 6 months post-palbociclib initiation) as a categoric variable as per section 8.1.2.

Proportion of patients experiencing febrile neutropenia and the worst grade of neutropenia experienced within 3-months of palbociclib initiation were also presented as a categoric variable as per section 8.1.2.

8.2.5 Secondary Objective 4: To describe the occurrence of gastro-intestinal toxicity, including diarrhoea, nausea and vomiting during the first-year post-initiation observation period.

Proposed: The proportion of patients developing diarrhoea, nausea and vomiting in their first year will summarised as a categorical variable (see section 8.1.2), while occurrences per patient will be summarised as a quantitative variable (see section 8.1.1). All the above will be assessed at 1, 15 and 22 days into the treatment cycle, for each cycle, as well as after 1 year of follow-up post-initiation of palbociclib.

[figure not shown]
Actual: Proportion of patients experiencing diarrhoea, nausea and vomiting as well as the associated grade were presented as categoric variables as per section 8.1.2. Proportion of patients experiencing an AE (at least one of neutropenia, diarrhoea, nausea, and vomiting) was presented as frequencies and proportions.

8.2.6 Secondary Objective 5: To describe progression of clinical indicators, including biochemical and radiological indicators at each time-point available during the first year following palbociclib treatment initiation (e.g., full blood counts, liver function tests, bone profile etc.).

Proposed: The first, mean, median, minimum, and maximum results per patient of all full blood counts, results of liver function tests and bone profile during the 6 months following palbociclib initiation will be summarised as quantitative variables (see section 8.1.1). For radiological indicators, proportions of patients with stable disease, progressive disease and who achieve CR/PR will be treated as binary variables (see section 8.1.3); the first or modal measurement will be used if there is more than one observation per patient. All the above will be assessed at 1, 15 and 22 days into the treatment cycle as well as after 1 year.

Actual: Baseline full blood counts, liver function tests, bone profile measurements and urea and electrolytes will be presented as quantitative variables as per section 8.1.1. To account for different number of test values in the 6 months post-palbociclib initiation, blood values were summarised per patient and then presented as quantitative variables as per section 8.1.1. Radiological indicators were presented as categoric variables as per section 8.1.2.

PFIZER CONFIDENTIAL

8.2.7 Secondary Objective 6: To describe BC-related healthcare resource utilisation (hospital admissions, outpatient visits and calls to CNS) during the first year following palbociclib initiation.

[figure not shown]
Proposed: The total number of inpatient, emergency department visits and outpatient visits will be calculated in the first year palbociclib initiation. The number of visits to each of these clinics per patient will be summarised as a quantitative variable (see section 8.1.1). Reasons for admission for each of these will be compiled and treated as a categorical variable (see section 8.1.2). For inpatient admissions, the proportion of visits that were planned/elective or non-elective/accident and emergency will be described using frequencies and percentages (see section 8.1.3). Length of stay per inpatient admission will be treated as a quantitative variable (see section 8.1.1). The number of phone calls to CNS will be compiled with the distribution of reasons analysed as a categorical variable (see section 8.1.2). The number of contacts with the AOS with distributions of reasons and types of contact (phone calls or visits) will also be compiled and displayed using a frequency table with percentages (see section 8.1.2).

Actual: Proportion of patients with at least one inpatient admission, reasons for admission, elective or non-elective admission were presented as a categoric variable as per section 8.1.2. Inpatient, outpatient, CNS and AOS interactions per patient as well as length of inpatient admission were presented as per quantitative variables as per section 8.1.1. All other endpoints were presented as categoric variables as per section 8.1.2.

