Secondary objective: To describe overall survival and progression-free survival, response (CR, PR), stable disease. This includes estimating the proportion of patients achieving those endpoints at 1, 2 and 3 years following palbociclib initiation; median survival, time to response and duration of response. In patients who respond to treatment, to describe PR and CR using "swimmer plots".

 Proportion of patients at 1, 2 and 3 years following initiation of palbociclib who: 
 Are free from disease progression. Are alive Achieved PR Achieved CR Had stable disease Median (95% confidence interval [CI]) : 
 PFS OS Time to achieving best overall response Summary measures of duration of response (Kaplan-Meier analysis). Representation of all radiological assessment of response (CR / PR / no response or stable disease / progressive disease) in patients responding to treatment (achieving CR or PR following initiation of palbociclib) using “swimmer plots”. 	
 Date ((DD/MM/YYYY) unless specified otherwise) of start and end of palbociclib. Date of data collection. Patient status at the end of data collection period (alive/dead): 
 Date of death / last clinic visit. If not known (i.e. lost to follow-up), date of last recorded hospital visit. Radiological assessments of response during the follow-up period: date of assessment and outcome (CR / PR / no response or stable disease / progressive disease), as documented by the local investigator.

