The following definitions will be implemented. PFS will be defined as the time from the date of palbociclib initiation to the date of first documented disease progression (i.e. mention of disease progression or mixed response in the medical records, e.g. due to evidence of a new site of disease, or increasing disease, after treatment initiation) or death. OS will be defined as the time from the date of palbociclib initiation until death from any cause. Time to achieving best overall response will be defined in patients who respond to treatment as the time from the date of palbociclib initiation until achievement of the best overall response: CR, or PR if CR is not achieved during follow-up. Duration of response will be defined as the time from the date CR or PR was first documented (whichever is recorded first) to the date of first documented disease progression or death from any cause (whichever occurs first).

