Definitions will be implemented as described in section 9.3 Variables. Patients who are known to be alive at the date of data collection (1-year for interim report and 3-year for full study report) will be censored at the date of data collection, and patients who are lost to follow-up will be censored on the date they were last known to be alive (e.g. date of last recorded hospital visit). Patients who are alive and free from disease progression at the date of data collection and those lost to follow-up will be censored on the date they were last known not to have disease progression (i.e. the date of last documented response assessment). Patients remaining in CR or PR at the end of the post-initiation observation period or lost to follow-up will be censored on the date CR or PR was last documented.

For the estimation of the proportion of patients alive, and free from disease progression, the denominator will be all patients known to be alive at the selected time-points (1 years, 2 years and 3 years). For the estimation of the proportion of patients achieving PR, CR and with stable disease at the selected time-points (1 years, 2 years and 3 years), the denominator will be all patients with at least one assessment of response (CR / PR / no response or stable disease / progressive disease) in the past year. Estimation of time to achieving best overall response and duration of response; and representation using swimmer plots will be performed in patients who respond (achieve CR or PR during follow-up) only.

Median PFS, OS, time to achieving best overall response, time to palbociclib dose modification and time to palbociclib discontinuation, and corresponding 95% CIs, will be estimated using Kaplan-Meier curves. Assessments of response (CR / PR / no response or stable disease / progressive disease) in patients responding to treatment (achieving CR or PR following initiation of palbociclib) will be represented using “swimmer plots”.

All percentages will be reported to the nearest whole number; therefore, in reporting study results in tables, figures and associated text, percentages may not add up to 100% due to rounding.

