- Summary measures of bone profile in the first 6 months following initiation:
 - Calcium.
 - Phosphate.
- Summary measures of urea and electrolytes in the first 6 months following initiation:
 - Creatinine
 - Potassium
 - Sodium
 - Urea
- Summary measures of radiological indicators in the first 6 months following initiation including the proportion of patients with:
 - Stable disease.
 - Progressive disease.
 - CR or PR.

Secondary Objective 6: To describe BC-related healthcare resource utilisation during the first year following palbociclib initiation.

- Summary measures of hospital admissions for each line of therapy, including:
 - Proportion of patients with at least one inpatient admission recorded
 - Inpatient admissions per patient.
 - Elective or non-elective.
 - Reasons for admission (including day cases).
 - Length of stay per inpatient admission.
 - Proportion of patients with at least one outpatient visit recorded
 - Outpatient visits per patient.
 - Reason for outpatient visit
 - Type of HCP seen during outpatient visits
- Proportion of patients with at least one interaction with CNS
- Number of CNS interactions per patient
- Type of CNS interaction
- Reason for CNS interaction
- Proportion of patients with at least one interaction with AOS
- Number of AOS interactions per patient
- Type of AOS interaction
- Reason for AOS interaction

For the estimation of endpoints, *the following definitions will be implemented. PFS will be defined as the time from the date of palbociclib initiation to the date of first documented disease progression (as documented in the radiological assessment section of the eCRF) or death. OS will be defined as the time from the date of palbociclib initiation until death from any cause. Time to achieving best overall response will be defined in patients who respond to treatment as the time from the date of palbociclib initiation until*

PFIZER CONFIDENTIAL

achievement of the best overall response: CR, or PR if CR is not achieved during follow-up. Duration of response will be defined as the time from the date CR or PR was first documented (whichever is recorded first) to the date of first documented disease progression or death from any cause (whichever occurs first).

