	during follow-up in Full Analysis set			date of CR/PR to documented disease progression or death. 95% confidence intervals calculated for median.	otherwise exclude.
Proportion of patients experiencing neutropenia and febrile neutropenia for first year post-observation period	Full Analysis set	Secondary objective 3	Overall and by grade of neutropenia. Treatment Line	Summary statistics calculated (incl. Mean/Median/SD/IQR/Range) and frequency and percentages of proportions of patients with neutropenia and febrile neutropenia.	Excluded
Proportion and summary measures of patients experiencing gastro-intestinal toxicity during first year observation period	Full Analysis set	Secondary objective 4	Overall and Treatment Line	Summary statistics calculated (incl. Mean/Median/SD/IQR/Range) and frequency and percentages of proportions of patients with experiencing gastro-intestinal toxicity including diarrhoea, nausea, and vomiting.	Excluded
Summary measures of full blood counts in the first year of initiation	Full Analysis set	Secondary objective 5	Overall and Treatment Line	Summary statistics calculated (incl. Mean/Median/SD/IQR/Range) of haemoglobin, white cell counts, absolute neutrophil counts, and platelet counts. The mean, median, minimum, and maximum reading will be used where multiple tests are taken within the study period.	Excluded
Summary measures of liver function tests in the first year following initiation of palbociclib	Full Analysis set	Secondary objective 5	Overall and Treatment Line	Summary statistics calculated (incl. Mean/Median/SD/IQR/Range) aspartate transaminase, alanine transaminase and alkaline phosphatase. The mean, median, minimum, and maximum reading will be used where multiple tests are taken within the study period.	Excluded
Summary measures of bone profile in the first year of initiation	Full Analysis set	Secondary objective 5	Overall and Treatment Line	Summary statistics calculated (incl. Mean/Median/SD/IQR/Range) of calcium and phosphate. The mean, median, minimum, and maximum reading will be used where multiple tests are taken within the study period.	Excluded
Summary measures of radiological indicators in the first year of initiation	Full Analysis set	Secondary objective 5	Overall and Treatment Line	Frequency and percentages for proportions of patients with stable and progressive disease or CR or PR. Where there is more than one test, the first, most common and most favourable test results will be used.	Excluded

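### Duration of response ends at progression or death, but its censoring rule goes back to the last recorded response, which can remove event-free time from responders later read as stable and bias the estimate short

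*SAP*

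**What the plan says.** **Event.** Protocol 9.3 starts the clock at the first response: "Duration of response will be defined as the time from the date CR or PR was first documented (whichever is recorded first"). SAP 6 repeats the definition and runs it "to the date of first documented disease progression or death from any cause (whichever occurs first"). The SAP 8.2.9 table specifies a Kaplan-Meier median from "date of CR/PR to documented disease progression or death. 95% confidence intervals calculated for median".

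**What is recorded.** Protocol 9.3 collects, for each radiological assessment, the "date of assessment and outcome (CR / PR / no response or stable disease / progressive disease), as documented by the local investigator". A response followed by a stable reading is therefore a sequence that the data can contain. It is not an event for this endpoint.

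**Censoring for response.** In SAP 8.2, responders who are still in CR or PR when observation ends "or lost to follow-up will be censored on the date CR or PR was last documented". Protocol 9.7 has the same rule: such patients "will be censored on the date CR or PR was last documented".

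**Censoring for freedom from progression.** The sentence just before it in SAP 8.2 covers patients alive without progression, and those lost to follow-up. They "will be censored on the date they were last known not to have disease progression (i.e., the date of last documented response assessment").

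**The concern.** The event and the censoring date answer different questions. The event is progression or death, so a responder read as stable is known to be event-free on the date of that scan. Going back to the last CR/PR record discards that knowledge.

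The loss falls on one side only. If the patient later progresses, the whole interval counts, including the stable period. If not, the interval is shortened, possibly to zero when the first response record is also the last. Time at risk then depends on what happens later, so censoring is informative and the Kaplan-Meier assumption fails. Risk sets shrink while the events stay, so the event-free curve is too low.

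Duration of response is part of a secondary objective in both documents. In a descriptive study the estimate itself is the product. A figure built this way would also fit poorly with progression-free survival, which uses the last assessment, and with the swimmer plots, which display stable disease.

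**Working it through.** The documents give no expected value for duration of response, so there is no planned figure to reproduce. The check has three steps.

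**1. Which responders lose time**

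| Event-free responder | Last-CR/PR rule | Last-assessment rule |
|---|---|---|
| Latest reading is CR or PR | Date of that reading | Same date, no loss |
| Latest reading stable, lost to follow-up | Last CR/PR, earlier | Latest stable reading |
| Latest reading stable, still followed | Earlier date only if still being in response is taken to mean not progressed; otherwise the sentence is silent | Latest stable reading |

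Only the second row is named by the wording without further interpretation. The third row depends on the reading.

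**2. Direction, by hand**

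Take eight responders: events at 6, 9, 12 and 15 months, and four event-free at 18 months. Kaplan-Meier multiplies (1 − events / number at risk) over the event times.

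- Last assessment: S(15) = 7/8 × 6/7 × 5/6 × 4/5 = 0.50.
- Two of the event-free patients moved back to a last CR/PR at 3 and 6 months: S(15) = 6/7 × 4/5 × 3/4 × 2/3 = 0.34.

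The same four events occur in both lines. Only the risk sets have changed.

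**3. Size, by simulation (200,000 responders per setting)**

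Every input is an assumption, because the documents give none:
- exponential time from first response to progression or death, true median 20 months, so true S(12) = 0.5^(12/20) = 0.66;
- scans every 3 months, with the event dated at the next scan;
- first response at month 6;
- follow-up to month 24, the 2-year horizon in SAP 5.1 and 8.1.

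*Broad reading: all event-free responders cut back, and a stable reading is permanent.*

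| Chance per scan of switching to stable | S(12), last assessment | S(12), last CR/PR | Fall, points |
|---|---|---|---|
| 10% | 0.66 | 0.61 | 5 |
| 20% | 0.66 | 0.55 | 11 |
| 30% | 0.66 | 0.49 | 17 |

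With first response at month 6, only 24 − 6 = 18 months can be observed. The median is then not reached under the last-assessment rule, but the last-CR/PR rule returns 18, 15 or 12 months.

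*Narrow readings, same base inputs.* If only lost-to-follow-up responders are cut back, the fall is 0.003 to 0.008. If stable readings alternate with CR/PR instead of being permanent, it is 0.00 to 0.003. With no stable readings the two rules coincide.

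*Sensitivity of the broad reading.*
- Follow-up to month 36 (SAP 8.2 still names 3 years), 10 and 20% per scan: S(12) falls from 0.66 to 0.63 and 0.60. The median falls from 21 to 18 months at both rates, and to 15 at 30%.
- True median 12 months, follow-up to month 24, 10% lost to follow-up: S(12) falls from 0.50 to 0.45 and 0.41 at 10 and 20% per scan. The median stays at 12 on the 3-month grid.

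*Strict reading with stable responders left out.* If an analyst finds no rule for responders who are stable at the end and drops them, S(12) falls from 0.66 to 0.55 and 0.45 at 10 and 20% per scan (true median 20 months, follow-up to month 24, 10% lost to follow-up).

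**The case against.** **The sentence does not name every event-free responder.** It names patients remaining in CR or PR, or lost to follow-up. On the plain words, a responder now read as stable and still followed is in neither group. The preceding sentence is not labelled as applying to progression-free survival only, and such a patient fits it. The requested rule may therefore already apply. This stands, and it rules out the reading that the plan cuts back every responder without an event. It does not remove the problem for responders lost after a stable reading: both sentences cover them and give different dates.

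**The large figures rest on unsupported inputs.** The switching rates, the 20-month median, the scan interval and the response time are all assumed. A permanent switch is an adverse case. This also stands: a reader might infer a demonstrated bias of 5 to 17 points, and the documents do not support that.

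**The analysis may not be reported.** SAP 6 says its list is meant to reflect the analyses carried out. The Secondary Objective 2 list there omits duration of response, and so does the account in SAP 8.2.3 of what was actually done. SAP 8.2 adds that some proposed analyses were dropped but kept on record. Yet the endpoint remains in the objectives (SAP 2.2), the definitions closing SAP 6 and the 8.2.9 table. Its status is unclear, which is a reason to settle it.

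**The stakes are limited.** This is one descriptive secondary summary in the responder subset, with no hypothesis or decision rule. Progression-free and overall survival have their own censoring rules and are unaffected.

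**Conclusion.** The concern holds in a limited form. The censoring date does not match the event. Where the last-CR/PR date is applied to a responder later read as stable, it removes known event-free time only from patients without an event, and the estimate is biased short. The wording does this directly for responders lost to follow-up after a stable reading. It does so for all stable event-free responders only if remaining in response is taken to mean not having progressed.

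Under the stated assumptions at 24 months, the fall in the 12-month estimate runs from under 1 point to about 5, 11 or 17 points. The upper figures need both the broad reading and a lasting switch to stable at 10, 20 or 30% per scan. The frequency of such switches is the deciding quantity, and the documents do not give it. The direction is secure; the size is not. The rule should be corrected, but the matter is of moderate weight.

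**What to change.** In protocol 9.7 and SAP 8.2, replace the response-specific sentence with one stating that responders without progression or death are censored at the last documented response assessment showing no progression, whether CR, PR or stable disease. This matches the rule for progression-free survival and leaves patients whose last reading is CR or PR unchanged. If time actually spent in CR or PR is the intended quantity, the definition should instead count loss of response as an event.

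Also reconcile the Secondary Objective 2 list in SAP 6 and the account in SAP 8.2.3 with the definition at the end of SAP 6 and the 8.2.9 table, so that it is clear whether duration of response is analysed. If it was dropped, say so.

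The cost is one sentence in each document, a correction to the SAP endpoint list or table, and one repeated Kaplan-Meier analysis if it has already been run. Assessment dates and outcomes are already among the collected variables, so no new data are needed. A count of responders whose last event-free reading is stable would show how much the change matters.
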